5.3.2.2 Handling/Processing of Samples

Specific instructions for collection of blood samples and subsequent preparation and storage of the plasma samples for pharmacokinetic assays of ombitasvir, possible ombitasvir metabolites, ABT-450, possible ABT-450 metabolites, SOF, GS-331007, ritonavir, and RBV (if applicable) will be provided by the central laboratory, AbbVie, or its designee.

5.3.2.3 Disposition of Samples

The frozen plasma samples for the pharmacokinetic assays of ombitasvir, possible ombitasvir metabolites, ABT-450, possible ABT-450 metabolites, ritonavir, SOF, GS-331007, RBV (if applicable), and archive plasma samples will be packed in dry ice sufficient to last during transport, and transferred from the study site to the central laboratory.

The central laboratory will then ship samples for the pharmacokinetic assays of ombitasvir, possible ombitasvir metabolites, ABT-450, possible ABT 450 metabolites, and RBV to:

Sample Receiving

c/o: Delivery Services
[name]
[name]

An inventory of the samples included will accompany the package and an electronic copy of the Manifests (including subject number, study day, the time of sample collection, and barcode) will be sent to the contact person at [contact].

The central laboratory will then ship samples for the pharmacokinetic assays of SOF, GS-331007, and other possible metabolites of SOF to reference laboratories following separately provided instructions.

An inventory of the SOF samples included will accompany the package and an electronic copy of the Manifests (including subject number, study day, and the time of sample collection) will be sent to [REDACTED].

5.3.2.4 Measurement Methods

The plasma concentration of ombitasvir, ABT-450, ritonavir, SOF, GS-331007 (predominant circulating metabolite of SOF), and RBV (if applicable), will be analyzed using validated assay methods under the supervision of the Drug Analysis Department at AbbVie. Plasma concentrations of possible metabolites of ombitasvir, ABT-450, and SOF (other than GS-331007) may also be determined using either validated or non-validated methods.

5.3.3 Efficacy Variables

Virologic response will be assessed by HCV RNA in IU/mL at various time points from Day 1 through 48 weeks after completion of treatment.

5.3.3.1 Primary Variable

The primary endpoint is the percentage of subjects with SVR₁₂ (HCV RNA < LLOQ 12 weeks after the last actual dose of study drug).

5.3.3.2 Secondary Variable

The secondary endpoints are:

- The percentage of subjects with virologic failure during treatment;
- The percentage of subjects with post-treatment relapse.

5.3.4 HCV Resistance Variables

The following resistance information will be provided for all subjects: the amino acid variants at baseline at signature resistance-associated positions identified by population nucleotide sequencing and comparison to the appropriate prototypic reference sequence.

The following resistance information will be analyzed for subjects who do not achieve SVR₁₂ and who have a post-baseline sample with HCV RNA \geq 1000 IU/mL: 1) the amino acid variants in available post-baseline samples identified by population and/or clonal nucleotide sequencing and comparison to the baseline sequence, 2) the amino acid variants in available post-baseline samples at signature resistance-associated positions identified by population nucleotide sequencing and comparison to the appropriate prototypic reference sequence, and 3) the persistence of resistance-associated amino acid variants by population and/or clonal nucleotide sequencing during the post-treatment period.

5.3.5 Safety Variables

The following safety evaluations will be analyzed during the study: adverse event monitoring and vital signs, physical examination, and laboratory test assessments.

5.3.6 Pharmacokinetic Variables

Plasma samples for ombitasvir, ABT-450, ritonavir, SOF, GS-331007 (predominant circulating metabolite of SOF), and RBV (if applicable) will be collected at each study visit up to 12 weeks. Individual plasma concentrations of possible metabolites of ombitasvir and ABT-450 may be measured and summarized if they are needed for additional safety or efficacy evaluation.

Values for the pharmacokinetic parameters of ombitasvir, ABT-450, ritonavir, SOF, GS-331007 (predominant circulating metabolite of SOF), and RBV (if applicable) including the C_{max} , T_{max} , C_{trough} , and AUC will be determined by noncompartmental methods using intensive pharmacokinetic blood sampling data in the study. Additional parameters or summaries may be determined if useful in the interpretation of the data.

5.3.7 Pharmacogenetic Variables

IL28B genotypes are associated with response to pegIFN and RBV and to some pegIFN-free regimens. IL28B status will be determined for each subject and analyzed as a factor contributing to the subject's response to study treatment. These IL28B genotype results may be analyzed as part of a multi-study assessment of IL28B and response to ombitasvir, ABT-450, and SOF.

DNA samples from subjects who separately consent for additional pharmacogenetic analysis may be sequenced and data analyzed for genetic factors contributing to the disease or subject's response to ombitasvir/ABT-450, or other study treatment, in terms of pharmacokinetics, efficacy, tolerability, and safety. Such genetic factors may include genes for drug metabolizing enzymes, drug transport proteins, genes within the target pathway, other genes believed to be related to the disease or to drug response (including IL28B). Some genes currently insufficiently characterized or unknown may be understood to be important at the time of analysis. The samples may be analyzed as part of a multi-study assessment of genetic factors involved in the response to ombitasvir/ABT-450, drugs of this class, or the disease state. The samples may also be used for the development of diagnostic tests related to ombitasvir/ABT-450 and SOF,

drugs of these classes, or the disease state. The results of pharmacogenetic analyses may not be reported with the study summary.

Messenger RNA samples from subjects who separately consent for the mRNA substudy may be analyzed for RNA expression levels contributing to the subject's response to study treatment in terms of pharmacokinetics, pharmacodynamics, efficacy, tolerability and safety. Analysis may include quantifying RNA levels from interferon-stimulated pathways or other families believed to be related to drug response. Messenger RNA analysis will be limited to studying response to HCV therapy; no other analyses will be performed.

5.4 Removal of Subjects from Therapy or Assessment

5.4.1 Discontinuation of Individual Subjects

Each subject has the right to withdraw from treatment or the study at any time. In addition, the investigator may discontinue a subject from treatment or the study at any time if the investigator considers it necessary for any reason, including the occurrence of an adverse event or noncompliance with the protocol.

If, during the course of study drug administration, the subject prematurely discontinues treatment, the procedures outlined for the applicable Premature D/C Visit should be completed as defined in [Table 4](#). It is recommended that this visit occur on the day of study drug discontinuation; however, this visit should occur within 2 days following their final dose of study drugs and prior to the initiation of any other anti-HCV therapy. However, these procedures should not interfere with the initiation of any new treatments or therapeutic modalities that the investigator feels are necessary to treat the subject's conditions. Following discontinuation of study drugs, the subject will be treated in accordance with the investigator's best clinical judgment. The date of the last dose of study drug and reason for discontinuation will be recorded in the eCRF. The subject should then begin the PT Period where the subject will be monitored for 48 weeks for safety, HCV RNA, the emergence and persistence of resistant viral variants, and assessments of PROs.

If a subject discontinues from the PT Period, the subject should return for post-treatment discontinuation procedures defined in [Table 5](#). The reason for discontinuation will also be recorded in the eCRF.

If a subject is discontinued from study drug (Treatment Period) or the PT Period with an ongoing adverse event or an unresolved laboratory result that is significantly outside the reference range, the investigator will attempt to provide follow-up until a satisfactory clinical resolution of the laboratory result or adverse event is achieved (Section [6.7](#)).

Subjects receiving a RBV-inclusive regimen who report a positive result is obtained on a pregnancy test during the Treatment Period must be notified to stop RBV immediately. Administration of DAAs may be continued at the investigator's discretion, if the benefit of continuing therapy is felt to outweigh the risk. Specific instructions regarding subject pregnancy can be found in Section [6.6](#). Subjects will continue to be monitored for SVR in the PT Period as described in Section [5.1.3](#). If the subject is receiving a RBV-containing regimen, the investigator is also encouraged to report the pregnancy information to the voluntary RBV Pregnancy Registry.

5.4.1.1 Virologic Failure Criteria for Subject Management

The following criteria will be considered evidence of virologic failure leading to discontinuation of study drug while receiving study drug and will be discontinued from study drug:

- Confirmed increase from nadir in HCV RNA (defined as 2 consecutive HCV RNA measurements of $> 1 \log_{10}$ IU/mL above nadir) at any time point during treatment; or
- Failure to achieve HCV RNA $<$ LLOQ by Week 8; or
- Confirmed HCV RNA \geq LLOQ (defined as 2 consecutive HCV RNA measurements \geq LLOQ) at any point during treatment after HCV RNA \leq LLOQ.

Confirmatory testing should be completed as soon as possible. Subjects should remain on study drug treatment until the virologic failure has been confirmed. If any of the above criteria are met, the subject will discontinue study drug treatment (Section [5.4.1](#)).

Subjects with HCV RNA < LLOQ at the end of treatment and who have a confirmed HCV RNA \geq LLOQ (defined as 2 consecutive HCV RNA measurements \geq LLOQ) at any point in the PT Period will be considered to have relapsed. Confirmation of an HCV RNA \geq LLOQ in the PT Period should be completed as soon as possible per Section [5.1.3](#).

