Study Population: Adult males and females at least 18 years of age with HCV genotype 3 infection without cirrhosis, who are treatment-naïve or previously treated with pegIFN, RBV, and/or SOF.

Number of Subjects to be Enrolled: Approximately 20 subjects.

Methodology:

This is a Phase 2, randomized, open-label, multicenter study evaluating the safety and efficacy of co-formulated ombitasvir/ABT-450/r co-administered with SOF with or without RBV in treatment naïve and prior (pegIFN, RBV, and/or SOF) treatment-experienced adults with genotype 3 HCV infection without cirrhosis. Approximately 20 subjects will be enrolled across approximately 8 sites globally into one of two arms.

The study consists of:

- **Treatment Period:** Approximately 20 subjects with genotype 3 HCV infection will be randomized 1:1 into the following treatment arms (approximately 10 subjects each):
 - **Arm A:** ombitasvir/ABT-450/r 25 mg/150 mg/100 mg once daily (QD) + SOF 400 mg QD for 12 weeks
 - **Arm B:** ombitasvir/ABT-450/r 25 mg/150 mg/100 mg QD + SOF 400 mg QD + RBV 1000 – 1200 mg divided twice daily (BID) for 12 weeks.Randomization to Arms A and B will be stratified by IL28B genotype (CC versus non-CC) and prior treatment status (treatment-naïve versus treatment-experienced). Study drugs should be administered with food. Subject safety laboratory results and virologic failure criteria will be evaluated during the Treatment Period. Upon completion of the Treatment Period or premature discontinuation, subjects will enter the Post-Treatment (PT) Period.
- **PT Period:** Subjects who complete or prematurely discontinue study drugs in the Treatment Period will be followed for 48 weeks to monitor safety, HCV RNA, the emergence and persistence of resistant viral variants, and assessments of Patient Report Outcomes (PROs).

Methodology (Continued):**Virologic Failure Criteria for Subject Management:**

The following criteria will be considered evidence of virologic failure. Subjects demonstrating any of the following will be discontinued from study drug:

- Confirmed increase from nadir in HCV RNA (defined as 2 consecutive HCV RNA measurements of $> 1 \log_{10}$ IU/mL above nadir) at any time point during treatment; or
- Failure to achieve HCV RNA $<$ LLOQ by Week 8; or
- Confirmed HCV RNA \geq LLOQ (defined as 2 consecutive HCV RNA measurements \geq LLOQ) at any point during treatment after HCV RNA $<$ LLOQ.

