Confirmatory testing, where required, should be completed as soon as possible. Also, when confirmation is required, the subject should remain on study treatment until the virologic failure has been confirmed.

If any of the above criteria are met on therapy, the subject will discontinue study treatment as described above.

All subjects who receive at least one dose of study drug in the Treatment Period will be monitored in the Post-Treatment Period for up to 48 weeks following the last dose of study drug.

Diagnosis and Main Criteria for Inclusion/Exclusion:**Main Inclusion:**

1. Male or female at least 18 years of age at time of screening.
2. Chronic HCV infection prior to study enrollment. Chronic HCV infection is defined as one of the following:
 - Positive for anti-HCV Antibody (Ab) or HCV RNA at least 6 months before Screening, and positive for HCV RNA and anti-HCV Ab at the time of Screening; or
 - HCV RNA $> 10,000$ IU/mL at the time of Screening with a liver biopsy consistent with chronic HCV infection (or a liver biopsy performed prior to enrollment with evidence of chronic hepatitis C disease).
3. Screening laboratory results from the central clinical laboratory indicating HCV genotype 3 infection only.
4. Subjects must be able to understand and adhere to the study visit schedule and all other protocol requirements and must voluntarily sign and date an informed consent.
5. Absence of cirrhosis, as documented by meeting one of the following criteria (per local standard practice):
 - Liver biopsy within 24 months prior to screening or during screening demonstrating the absence of cirrhosis.
 - Only in the absence of a biopsy within the 24 months prior to screening or during screening:
 - a screening FibroTest score of ≤ 0.72 and Aspartate Aminotransferase to Platelet Ratio Index (APRI) ≤ 2 ; or
 - a screening transient elastography (e.g., FibroScan[®]) result of < 12.5 kPa.

Diagnosis and Main Criteria for Inclusion/Exclusion (Continued):**Main Inclusion(Continued):**

Subjects with a FibroScan® result that is ≥ 12.5 kPa and < 14.6 kPa, **or** a FibroTest result that is ≤ 0.72 and an APRI ≥ 2 , **or** a FibroTest result that is > 0.73 and an APRI ≤ 2 , must have a liver biopsy performed within 24 months prior to screening showing no evidence of cirrhosis, or in the absence of an available biopsy results within 24 months prior to screening, may undergo a liver biopsy during screening to rule out cirrhosis.

Main Exclusion:

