10.0 Efficacy Analysis

10.1 General Considerations

Analyses will be performed on the intent-to-treat (ITT) population. Sensitivity analyses of the primary endpoint, when applicable, will be performed on the mITT-GT-VF population specified in Section 5.1.1.

Missing data will be imputed as described in Section 6.3 for analyses of the HCV RNA endpoints of SVR.

Plasma HCV RNA levels will be determined for each sample collected by the central laboratory using the Roche COBAS TaqMan® real-time reverse transcriptase-PCR (RT-

PCR) assay v.2.0. For this assay, the lower limit of quantitation (LLOQ) is 25 IU/mL regardless of genotype, and the lower limit of detection (LLOD) varies by genotype. For GT3, the lower limit of detection (LLOD) is 20 IU/mL; for GT2, LLOD is 20 IU/mL. HCV RNA results that are detectable but not quantifiable are reported as "< 25 IU/mL HCV RNA detected" and those that are undetectable are reported as "HCV RNA not detected" in the database.

The notation "HCV RNA < LLOQ" is used to represent all HCV RNA values < 25 IU/mL, including values reported as "HCV RNA not detected" or "< 25 IU/mL HCV RNA detected." HCV RNA \geq LLOQ are all quantifiable values of 25 IU/mL or greater.

IL28B rs12979860 will be resulted as C/C, C/T, or T/T by the central laboratory.

Definitions for Efficacy Endpoints

Note that a confirmed quantifiable post-treatment value is defined as two consecutive post-treatment HCV RNA measurements \geq LLOQ. During treatment, a confirmed quantifiable value is defined as any two consecutive HCV RNA values \geq LLOQ, either both during treatment or at the final treatment measurement and the next consecutive post-treatment measurement.

Breakthrough = confirmed HCV RNA \geq LLOQ after HCV RNA < LLOQ during treatment, or confirmed increase from nadir in HCV RNA (two consecutive HCV RNA measurements $> 1 \log_{10}$ IU/mL above nadir) at any time point during treatment. A single breakthrough value (\geq LLOQ or $> 1 \log_{10}$ IU/mL above nadir) followed by lost to follow-up will be considered a breakthrough (i.e., will not require confirmation).

On-treatment virologic failure = breakthrough or failure to suppress during treatment (all on-treatment values of HCV RNA \geq LLOQ) with at least 6 weeks (defined as study drug duration \geq 36 days) of treatment for 12-week and 8-week treatment or at least 26 days of treatment for 6-week treatment.

RVR (rapid virologic response) = HCV RNA < LLOQ in the Week 4 window.

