HCV re-infection is defined as confirmed HCV RNA \geq LLOQ after the end of treatment in a subject who had HCV RNA $<$ LLOQ at Final Treatment Visit, along with the post-treatment detection of a different HCV genotype, subtype, or clade compared with baseline, as determined by phylogenetic analysis of the NS3 or NS5A, and/or NS5B gene sequences. Re-infection in the case of the same HCV subtype is defined as a clade switch, as indicated by the lack of clustering between the baseline and post-treatment sequences by phylogenetic analysis. If phylogenetic analysis is not possible due to technical difficulties, HCV re-infection may be determined with a confirmed HCV genotype or subgenotype switch by the Versant HCV Genotype Inno-LiPA Assay v2.0 or Sanger assay.

Reasons for SVR₁₂ Non-Response

Subjects who do not achieve SVR₁₂ (SVR₁₂ non-responders) will be categorized as having:

1. On-treatment virologic failure (see **On-treatment virologic failure** definition);
2. Relapse (defined according to the **Relapse₁₂** definition for subjects who complete treatment);
3. Prematurely discontinued study drug with no on-treatment virologic failure (defined as any SVR₁₂ non-responder who prematurely discontinued study drug (duration $<$ 77 days, $<$ 49 days, and $<$ 38 days for 12 week, 8 week, and 6 week treatment regimens) and did not meet the **On-treatment virologic failure definition**);

4. HCV re-infection (see definition described earlier);
5. Missing follow-up data in the SVR₁₂ window (defined as any subject who completed study drug without data in the SVR₁₂ window and not meeting the definitions of [1], [2], [3], or [4]);
6. Other (defined as any SVR₁₂ non-responder not meeting the definitions of [1] – [5], such as a subject with a single quantifiable value within the SVR₁₂ window followed by an undetectable value beyond the SVR₁₂ window).

Reasons for SVR₂₄ Non-Response

Subjects who do not achieve SVR₂₄ (SVR₂₄ non-responders) will be categorized as having:

1. On-treatment virologic failure (see **On-treatment virologic failure definition**);
2. Relapse (defined according to the **Relapse₁₂** definition for subjects who complete treatment);
3. Relapsed after achieving SVR₁₂ (see **Relapse₂₄**);

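### Synopsis and Protocol 5.4.1.1 differ on whether Week 8 non-suppression is confirmed before drug is stopped, and in a narrow case a subject withdrawn under that criterion leaves the SVR12 sensitivity population as a non-virologic dropout

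*Protocol*

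**What the plan says.** **Stopping rule.** The synopsis and Protocol 5.4.1.1 give the same three on-treatment criteria. Rise from nadir and return to quantifiable RNA are each labelled confirmed and defined by two consecutive measurements. The second criterion, "Failure to achieve HCV RNA" below LLOQ by Week 8, has neither the label nor a two-measurement definition.

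**Confirmation.** The synopsis is conditional: "Confirmatory testing, where required, should be completed as soon as possible", and "when confirmation is required, the subject should remain on study treatment until the virologic failure has been confirmed". Section 5.4.1.1 has no such condition: "Subjects should remain on study drug treatment until the virologic failure has been confirmed".

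**Endpoint.** SAP 10.1 defines "On-treatment virologic failure = breakthrough or failure to suppress during treatment". Failure to suppress means that every on-treatment value is at or above LLOQ (25 IU/mL), with at least 36 days of drug in the 12-week arms. Protocol 8.1.2.2 uses the same definition. Neither mentions Week 8.

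**Reasons for SVR12 non-response.** SAP 10.1 has a category "Prematurely discontinued study drug with no on-treatment virologic failure", which in the 12-week arms covers non-responders with under 77 days of drug who do not meet the endpoint above. SAP 5.1.1 removes from mITT-GT-VF those who missed SVR12 for reasons other than virologic failure. SAP 10.5 runs its sensitivity analysis of the primary endpoint on that population only.

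**The concern.** There are two separate problems.

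The first is operational. A subject still quantifiable at Week 8 can be stopped on that result under the synopsis, or kept on drug pending a repeat under 5.4.1.1. Section 5.6.1 says that durations under 12 weeks are predicted to give more relapses, so the passage a site follows may affect that subject's outcome.

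The second is analytic. The stopping rule looks at whether the subject had suppressed by Week 8. The endpoint looks at all on-treatment values, including any sample taken at withdrawal. A subject can therefore be withdrawn for virologic failure without being one in the analysis. The mITT-GT-VF population is meant to remove non-virologic failures, so removing this subject makes the sensitivity SVR12 look better than the virologic outcome.

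**Working it through.** **1. The two passages side by side**

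| Element | Synopsis 1.1 | Section 5.4.1.1 |
|---|---|---|
| Nadir and rebound criteria | two consecutive values | two consecutive values |
| Week 8 criterion | not defined as confirmed | not defined as confirmed |
| Repeat test | only where required | stated without condition |
| Staying on drug until confirmed | only when confirmation is required | stated without condition |
| Stop drug | when any criterion is met | when any criterion is met |

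Take an illustrative subject at or above 25 IU/mL at Weeks 1, 2 and 4, with 30 IU/mL at Week 8. Under the synopsis the criterion is met and drug stops. Read literally, 5.4.1.1 keeps the subject on drug until a repeat confirms the result. Section 5.4.1.1 is unclear even alone, because it also says drug stops once any listed criterion is met.

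**2. Tracing a withdrawn subject through the definitions**

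Inputs:
- Week 8 analysis window: Study Days 43 to 63 (SAP Table 2).
- HCV RNA is sampled at the premature discontinuation visit (Protocol Table 4), due within 2 days of the last dose (Protocol 5.4.1).
- A value up to Study Drug End Day 2 counts as on treatment (SAP 6.1.2).
- Failure to suppress: all on-treatment values ≥ 25 IU/mL and duration ≥ 36 days (Protocol 8.1.2.2, SAP 10.1).
- Relapse12 needs duration ≥ 77 days (Protocol 8.1.2.2, SAP 10.4).

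The subject is never below LLOQ through Week 8, is withdrawn under the rule, and later misses SVR12. The definitions were applied at withdrawal on Days 43, 50, 56, 58, 63, 70 and 76:

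| Test | Last on-treatment sample ≥ 25 | Last on-treatment sample < 25 |
|---|---|---|
| All on-treatment values ≥ LLOQ, ≥ 36 days | met | not met |
| Breakthrough | not needed | not met: no quantifiable on-treatment value follows the one < LLOQ |
| Relapse12 | not applicable | barred, < 77 days |
| Reason for non-response | on-treatment virologic failure | premature discontinuation, no on-treatment virologic failure |
| In mITT-GT-VF | yes | no |

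The result is the same on every day tested. The 36-day threshold excludes nobody here, because the Week 8 window opens on Day 43.

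**3. Size**

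The Wilson 95% interval for x/n, with p = x/n, z = 1.96 and z² = 3.8415, is

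[p + z²/(2n) ± z·√(p(1−p)/n + z²/(4n²))] / (1 + z²/n).

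- Plan's own figure, 9/10: centre (0.9 + 0.1921)/1.3842 = 0.789; half-width 1.96·√(0.0090 + 0.0096)/1.3842 = 0.193; interval 59.6% to 98.2%. This reproduces Protocol 8.2 and SAP 4.3.
- 9/9: the upper limit is 100% and the lower limit is 1/(1 + 3.8415/9) = 1/1.4268 = 70.1%.

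If this subject is the only SVR12 failure among 10, mITT-GT-VF SVR12 is 9/9 (70.1–100%) as the SAP stands and 9/10 (59.6–98.2%) if the subject counts as a virologic failure. ITT SVR12 is 9/10 under both.

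**The case against.** The strongest reply has four parts.

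- **The passages can be read together.** Only two criteria are labelled confirmed, so the unqualified sentence in 5.4.1.1 may refer only to them. That is a fair reading, but the text does not say so.
- **The Week 8 criterion is not one isolated value.** It is met only if no earlier sample was below LLOQ either. This is correct, but the last of those results still carries no confirmation requirement, and it is the one that triggers withdrawal.
- **A management rule need not equal an endpoint.** This stands. A reader might infer that the on-treatment failure rate is wrong, at 0/10 (Wilson 0–27.8%) where it should be 1/10 (1.8–40.4%). The documents do not support that: the endpoint is explicitly laboratory-defined, and a subject with an on-treatment value below LLOQ did suppress. Making any withdrawal under 5.4.1.1 an endpoint event could also score a subject who goes on to reach SVR12 as a failure.
- **The subject remains visible.** SAP 8.0 tabulates discontinuation reasons, SAP 10.1 summarises overall relapse in those who stopped early, and SAP 10.6 lists preterm relapses among non-completers whose final value was below LLOQ. This is true, but none of these changes the non-response category or membership of mITT-GT-VF.

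A reader might also object that a subject stopping for another reason on Days 36 to 55, still quantifiable, counts as on-treatment failure before Week 8 is reached. That is an explicit choice in the endpoint definition, not an error.

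**Conclusion.** Both parts hold, at modest size.

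The confirmation wording differs within the supplied protocol and must be reconciled. Its effect on SVR12 cannot be quantified from the documents.

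The misclassification is real but narrow. It needs a last on-treatment sample below LLOQ after the Week 8 result; the ordinary Week 8 non-suppressor is classified correctly. It arises most readily under the synopsis reading. Under 5.4.1.1 read literally, it needs a confirmed result followed by a discontinuation sample below LLOQ. Its frequency is unknown. One such subject moves sensitivity SVR12 between 9/9 and 9/10 in a 10-subject arm. A reader might infer that the primary result is at risk from the classification; it is not, because ITT SVR12 does not use the reason for failure.

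Two assumptions matter. First, virologic failure in the mITT-GT-VF definition is taken to mean the virologic categories in the SAP 10.1 reasons list, since SAP 5.1.1 does not define it. Second, the SAP covers Arms A to F and about 70 subjects, so it follows a later protocol than the one supplied. SAP 10.7 equates the virologic stopping criteria with failure to suppress by Week 6, which may reflect an amended rule. The difference between the synopsis and 5.4.1.1, and the mismatch between the Week 8 rule and the endpoint in Protocol 8.1.2.2, do not depend on this.

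**What to change.** 1. Reconcile synopsis 1.1 and Protocol 5.4.1.1 so that both say the same thing about whether the Week 8 criterion needs confirmation before drug is stopped. Which rule to keep is for the clinical team.
2. Check the stopping rule in the protocol version that the SAP follows, given the Week 6 wording in SAP 10.7.
3. Leave the laboratory-defined on-treatment failure endpoint unchanged. In the SAP 10.1 reasons for SVR12 non-response, ahead of the premature discontinuation category, class as a virologic failure any SVR12 non-responder whose drug was stopped because a Protocol 5.4.1.1 criterion was met, as shown by the HCV RNA data and the eCRF reason. State in SAP 5.1.1 that such subjects stay in mITT-GT-VF.

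Limiting item 3 to SVR12 non-responders means nobody is both a responder and a failure. Requiring the HCV RNA data as well as the eCRF reason limits reliance on site judgement.

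The cost is a wording change in the protocol and two short clauses in the SAP, with no new data. The sensitivity SVR12 may come out slightly less favourable.
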